4.0 PATIENT ELIGIBILITY

4.1 Phase I

4.1.1 Inclusion Criteria

- 4.1.1.1** Patients must have cytologically or histologically confirmed relapsed or refractory extensive-disease small-cell lung cancer (ES-SCLC) or non-progressing ES-SCLC after first line chemotherapy, or advanced or inoperable grade I-II pulmonary NETs.
- 4.1.1.2** Patients with tumor tissue uptake during NETSPOT[®] PET that is equal to or higher than that in normal hepatic tissue (grade ≥ 2) will be eligible. At the discretion of the principal investigator, patients with SCLC whose tumors have lower levels of uptake than liver during NETSPOT[®] PET may be eligible for the study.
- 4.1.1.3** Toxicities of prior therapy must be resolved to grade 1 or less as per Common Terminology Criteria for Adverse Events (CTCAE) version 4.03 with the exception of alopecia and grade 2, prior platinum-therapy related neuropathy.
- 4.1.1.4** Prior chemotherapy, radiotherapy or radiosurgery (including prophylactic cranial radiation and/or thoracic radiation) must have been completed at least 2 weeks prior to study treatment.
- 4.1.1.5** ECOG performance status of 0-1.
- 4.1.1.6** Adequate organ and bone marrow function (hemoglobin > 9 g/dL; absolute neutrophil count $> 1.5 \times 10^9/L$; platelet counts $> 100 \times 10^9/L$; serum bilirubin $< 2 \times$ ULN (except subjects with Gilbert Syndrome who must have total bilirubin < 3.0 mg/dL); alanine aminotransferase (ALT) and aspartate aminotransferase (AST) $< 2.5 \times$ ULN or $< 5 \times$ ULN if liver metastases; calculated creatinine clearance > 50 mL/min).
- 4.1.1.7** Life expectancy of at least 3 months.
- 4.1.1.8** Age > 18 years.
- 4.1.1.9** Women of childbearing potential (WOCBP) must use appropriate method(s) of contraception for 23 weeks after the last dose of investigational drug. Men who are sexually active with WOCBP must use any contraceptive method(s) with a failure rate of less than 1% per year for 31 weeks after the last dose of investigational drug. Women who are not of childbearing potential (i.e., who are postmenopausal or surgically sterile as well as azoospermic men) do not require contraception. Should a woman become pregnant or suspect she is pregnant while she or her partner is participating in this study, she should inform her treating physician immediately. See Section 4.3 for the definition of WOCBP.

4.1.1.10 Women of childbearing potential must have a negative serum or urine pregnancy test (minimum sensitivity 25 IU/L or equivalent units of human chorionic gonadotropic [HCG]) within 24 hours prior to the start of the study drug.

4.1.1.11 Women must not be pregnant or breastfeeding.

4.1.1.12 Ability to understand and willingness to sign a written informed consent document.

4.1.2 Exclusion Criteria

4.1.2.1 Subjects with active, known or suspected autoimmune disease. Subjects with vitiligo, type I diabetes mellitus, residual hypothyroidism due to autoimmune condition only requiring hormone replacement, psoriasis not requiring systemic treatment, or conditions not expected to recur in the absence of an external trigger are permitted to enroll.

4.1.2.2 Subjects with a condition requiring systemic treatment with either corticosteroids (> 10 mg daily prednisone equivalents) or other immunosuppressive medications within 14 days of study drug administration. Inhaled or topical steroids, and adrenal replacement doses > 10 mg daily prednisone equivalents are permitted in the absence of active autoimmune disease.

4.1.2.3 Subjects with symptomatic brain metastases will be excluded. However, subjects who have had treatment for their brain metastasis and are asymptomatic without steroid therapy for at least 2 weeks may be enrolled.

4.1.2.4 Prior treatment with an anti-PD-1, anti-PD-L1, anti-PD-L2, anti-CTLA-4 antibody, or any other antibody or drug specifically targeting T-cell costimulation or immune checkpoint pathways.

4.1.2.5 Treatment with investigational agents is prohibited from 30 days prior to the first dose of the study treatment, and throughout the study.

4.1.2.6 History of a previous malignancy within the last 2 years, with the exception of early stage cancers that are at very low risk of recurrence, such as non-melanoma skin cancer, papillary carcinoma of the thyroid, or carcinoma in situ of the prostate, cervix, or breast.

4.1.2.7 Patients with human immunodeficiency virus (HIV) infection, or active hepatitis B or C virus infection will be excluded.

4.1.2.8 Patients who received prior anti-tumoral radionuclide therapy (with unsealed sources) are not eligible for the study.

4.1.2.9 Prior major surgery within 12 weeks or prior major surgery from which the patient has not sufficiently recovered yet.

- 4.1.2.10** Logistical or psychological hindrance to participation in clinical research.
- 4.1.2.11** Uncontrolled or significant cardiovascular disease, including any of the following:
- Symptomatic congestive heart failure (\geq New York Heart Association Classification Class II).
 - Cerebral vascular accident/stroke (< 6 months prior to enrollment), myocardial infarction (< 6 months prior to enrollment), or unstable angina.
 - Uncontrolled hypertension or uncontrolled cardiac arrhythmia.
- 4.1.2.12** Any other medical condition that in the Investigator's opinion would not make the patient a good candidate for the study.

4.2 Phase II

4.2.1 Inclusion Criteria

- 4.2.1.1** Patients must have cytologically or histologically confirmed ES-SCLC and must not have progressed after first line platinum-based chemotherapy regimen before randomization.
- 4.2.1.2** Patients with tumor tissue uptake during NETSPOT[®] PET that is equal to or higher than that in normal hepatic tissue (grade ≥ 2) will be eligible. It is recommended that NETSPOT[®] PET be obtained before initiation of chemotherapy, but NETSPOT[®] PET obtained during or after completion of chemotherapy could be used for screening purpose.
- 4.2.1.3** Toxicities of prior therapy must be resolved to grade 1 or less as per Common Terminology Criteria for Adverse Events (CTCAE) version 4.03 with the exception of alopecia and grade 2, prior platinum-therapy related neuropathy.
- 4.2.1.4** Prior radiotherapy or radiosurgery (including prophylactic cranial radiation and/or thoracic radiation) must have been completed at least 2 weeks prior to randomization.
- 4.2.1.5** For patients who do not receive radiotherapy after chemotherapy, the randomization must occur within 6 weeks of the last chemotherapy cycle. The study treatment must start within 2 weeks from randomization and no less than 2 weeks from last chemotherapy dose. For patients who receive radiotherapy (including prophylactic cranial radiation and/or thoracic radiation) after chemotherapy, the randomization must occur at least 8 weeks after completion of radiation therapy but within 12 weeks after completion of radiation therapy.
- 4.2.1.6** ECOG performance status of 0-1.

- 4.2.1.7** Adequate organ and bone marrow function (hemoglobin > 9 g/dL; absolute neutrophil count > $1.5 \times 10^9/L$; platelet counts > $100 \times 10^9/L$; serum bilirubin < 2 x ULN (except subjects with Gilbert Syndrome who must have total bilirubin < 3.0 mg/dL); alanine aminotransferase (ALT) and aspartate aminotransferase (AST) < 2.5 x ULN or < 5 x ULN if liver metastases; calculated creatinine clearance > 50 mL/min).
- 4.2.1.8** Life expectancy of at least 3 months.
- 4.2.1.9** Age > 18 years.
- 4.2.1.10** Women of childbearing potential (WOCBP) must use appropriate method(s) of contraception for 23 weeks after the last dose of investigational drug. Men who are sexually active with WOCBP must use any contraceptive method(s) with a failure rate of less than 1% per year for 31 weeks after the last dose of investigational drug. Women who are not of childbearing potential (i.e., who are postmenopausal or surgically sterile as well as azoospermic men) do not require contraception. Should a woman become pregnant or suspect she is pregnant while she or her partner is participating in this study, she should inform her treating physician immediately. See Section 4.3 for the definition of WOCBP.
- 4.2.1.11** Women of childbearing potential must have a negative serum or urine pregnancy test (minimum sensitivity 25 IU/L or equivalent units of human chorionic gonadotropic [HCG]) within 24 hours prior to the start of the study drug.
- 4.2.1.12** Women must not be pregnant or breastfeeding.
- 4.2.1.13** Ability to understand and willingness to sign a written informed consent document.

4.2.2 Exclusion Criteria

- 4.2.2.1** Subjects with active, known or suspected autoimmune disease. Subjects with vitiligo, type I diabetes mellitus, residual hypothyroidism due to autoimmune condition only requiring hormone replacement, psoriasis not requiring systemic treatment, or conditions not expected to recur in the absence of an external trigger are permitted to enroll.
- 4.2.2.2** Subjects with a condition requiring systemic treatment with either corticosteroids (> 10 mg daily prednisone equivalents) or other immunosuppressive medications within 14 days of study drug administration. Inhaled or topical steroids, and adrenal replacement doses > 10 mg daily prednisone equivalents are permitted in the absence of active autoimmune disease.
- 4.2.2.3** Subjects with symptomatic brain metastases will be excluded from trial secondary to poor prognosis. However, subjects who have had treatment for their brain metastasis and whose brain disease is stable without steroid therapy for 2 weeks may be enrolled.

- 4.2.2.4 Prior treatment with an anti-PD-1, anti-PD-L1, anti-PD-L2, anti-CTLA-4 antibody, or any other antibody or drug specifically targeting T-cell costimulation or immune checkpoint pathways.
- 4.2.2.5 Treatment with investigational agents is prohibited from 30 days prior to the first dose of the study treatment, and throughout the study.
- 4.2.2.6 History of a previous malignancy within the last 2 years, with the exception of early stage cancers that are at very low risk of recurrence, such as non-melanoma skin cancer, papillary carcinoma of the thyroid, or carcinoma in situ of the prostate, cervix, or breast.
- 4.2.2.7 Patients with human immunodeficiency virus (HIV) infection, or active hepatitis B or C virus infection will be excluded.
- 4.2.2.8 Patients who received prior anti-tumoral radionuclide therapy (with unsealed sources) are not eligible for the study.
- 4.2.2.9 Prior major surgery within 12 weeks or prior major surgery from which the patient has not sufficiently recovered yet.
- 4.2.2.10 Logistical or psychological hindrance to participation in clinical research.
- 4.2.2.11 Uncontrolled or significant cardiovascular disease, including any of the following:
 - Symptomatic congestive heart failure (\geq New York Heart Association Classification Class II).
 - Cerebral vascular accident/stroke ($<$ 6 months prior to enrollment), myocardial infarction ($<$ 6 months prior to enrollment), or unstable angina.
 - Uncontrolled hypertension or uncontrolled cardiac arrhythmia.
- 4.2.2.12 Any other medical condition that in the Investigator's opinion would not make the patient a good candidate for the study.

4.3 WOCBP/MOCBP

Women of childbearing potential (WOCBP) is defined as any female who has experienced menarche and who has not undergone surgical sterilization (hysterectomy or bilateral oophorectomy) or is not postmenopausal. Menopause is defined clinically as 12 months of amenorrhea in a woman over age 45 in the absence of other biological or physiological causes. In addition, women under the age of 62 must have a documented serum follicle stimulating hormone, (FSH) level $>$ 40 mIU/mL. Women treated with hormone replacement therapy (HRT) are likely to have artificially suppressed FSH levels and may require a washout period in order to obtain a physiologic FSH level. The duration of the washout period is a function of the type of HRT used:

- 1-week minimum for vaginal hormonal products, (rings, creams, gels)

- 4-week minimum for transdermal products
- 8-week minimum for oral products.

Other parenteral products may require washout periods as long as 6 months.

Women of childbearing potential (WOCBP) must agree to follow instructions for acceptable contraception from the time of signing consent, and for 23 weeks after their last dose of protocol-indicated treatment.

Men not azoospermic who are sexually active with WOCBP must agree to follow instructions for acceptable contraception from the time of signing consent, and for 31 weeks after their last dose of protocol-indicated treatment.

5.0 TREATMENT PLAN

5.1 Treatment Dosage and Administration

5.1.1 Phase I

5.1.1.1 Dose Limiting Toxicity (DLT)

A DLT is defined as any toxicity not attributable to the disease or disease-related processes under investigation, which occurs from the first dose of study treatment (Day 1, Cycle 1) up to the last day of the cycle (Day 57). To be considered as DLT, it must be related to the study drugs (attributions: possible, probable, and definite) while fulfilling one of the following criteria as per the NCI Common Toxicity Criteria for Adverse Events (CTCAE) version 4.03:

- Toxicity grade 2 for platelets and any other grade 3 or 4 toxicity, excluding
 - Grade 3 diarrhea, nausea, or vomiting if it can be controlled with supportive therapy
 - Grade 3 endocrinopathy that is managed with or without systemic corticosteroid therapy and/or hormone replacement therapy and the patient is asymptomatic.
- Persistent (>21 days) non-hematologic grade 2 adverse events despite optimal medical management and treatment delay > 21 days
- Any other toxicity:
 - if worse than baseline value, documented, clinically relevant and/or unacceptable, and is judged to be a DLT by the investigators
 - if results in a protocol defined stopping criteria
 - if results in disruption of dosing schedule

Patients experiencing DLT will be monitored weekly until toxicity stabilization, and then every two weeks until normalization.

5.1.1.2 Dose Escalation and Treatment Duration

Treatment will be administered on an outpatient basis.

A standard dose-escalation phase I design will be used. Three subjects will be enrolled at each

dose level in the absence of DLT. Please find the details in the dose escalation table below.

Dose escalation table

Number of Patients with DLT at a Given Dose Level	Escalation Decision Rule
0 out of 3	Enter 3 patients at the next dose level.
≥ 2	Dose escalation will be stopped. This dose level will be declared the maximally administered dose (highest dose administered). Three additional patients will be entered at the next lowest dose level if only 3 patients were treated previously at that dose.
1 out of 3	Enter at least 3 more patients at this dose level. 
 • If 0 of these 3 patients experience DLT, proceed to the next dose level. • If 1 or more of this group suffer DLT, then dose escalation is stopped, and this dose is declared the maximally administered dose. • Three additional patients will be entered at the next lowest dose level if only 3 patients were treated previously at that dose.
≤ 2 out of 6 at highest DL	This is generally the recommended phase 2 dose. At least 6 patients must be treated at the recommended phase 2 dose.

Selection of the starting dose of $^{177}\text{Lu-DOTA}^0\text{-Tyr}^3\text{-Octreotate}$ and nivolumab is based on the results from previous clinical studies with each compound used as single agent and the fact that the combination has not been tested in clinical trials. The first dose of $^{177}\text{Lu-DOTA}^0\text{-Tyr}^3\text{-Octreotate}$ will be given two weeks after the first administration of nivolumab. Studies have shown that intravenous administration of amino acids has a renal protective effect [46]. An infusion of amino acids will be started 30 minutes before the administration of $^{177}\text{Lu-DOTA}^0\text{-Tyr}^3\text{-Octreotate}$ and last 4 hours (Table 3).

Patient Replacement

Three patients within a dose level must be observed for one cycle (56 days) before accrual to the next higher dose level may begin. If a patient is withdrawn from the study prior to completing 56 days of therapy without experiencing a DLT prior to withdrawal, an additional patient may be added to that dose level.

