5.3.1 General Recommendations for Evaluation of Toxicities and Dose Delays/Modifications

Any patient who receives treatment on this protocol will be evaluable for toxicity. Toxicity will be assessed according to the NCI Common Toxicity Criteria for Adverse Events (CTCAE), version 4.03. Dose delays or dose modifications should be made according to the system showing the greatest degree of toxicity. Once the patient has a dose reduction due to toxicity, the dose will not

be re-escalated. Dose delays and dose modifications will be made using the following recommendations. At the discretion of the investigator, the study drugs may be held or dose modified independently if the observed AE is attributed to only one of the study drugs, while the patient continued to receive the drug not associated with the observed AE. For example, if the patient develops immune-related adverse events, nivolumab may be held following guidelines in section 5.3.5 while the patient continues to receive $^{177}\text{Lu-DOTA}^0\text{-Tyr}^3\text{-Octreotate}$. If the patient develops hematologic adverse events that are frequently associated with $^{177}\text{Lu-DOTA}^0\text{-Tyr}^3\text{-Octreotate}$, but rarely associated with nivolumab (e.g. thrombocytopenia), $^{177}\text{Lu-DOTA}^0\text{-Tyr}^3\text{-Octreotate}$ may be held while the patient continues on nivolumab. If the observed toxicity is attributable to both drugs, both drugs will be held.

Dose modifications for $^{177}\text{Lu-DOTA}^0\text{-Tyr}^3\text{-Octreotate}$ are permitted according to the table below.

Dose Level (DL)	$^{177}\text{Lu-DOTA}^0\text{-Tyr}^3\text{-Octreotate}$ (IV)
Level 1	3.7 GBq (100 mCi) every 8 weeks
Level 2	7.4 GBq (200 mCi) every 8 weeks

No dose modifications are allowed for nivolumab.

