*Values calculated assuming ¹⁷⁷Lu specific activity of 740 GBq/mg at labelling time and a mean synthesis yield of █ and radiochemical purity █

Treatment with ¹⁷⁷Lu-DOTA⁰-Tyr³-Octreotate will consist of a cumulative dose of 14.8 GBq (400 mCi) or 29.6 GBq (800mCi) with the dosing equally divided among 4 administrations of ¹⁷⁷Lu-DOTA⁰-Tyr³-Octreotate at 8±1-weeks intervals.

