11.0 STATISTICAL CONSIDERATIONS

11.1 Study Design

This is a phase I/II clinical trial of $^{177}\text{Lu-DOTA}^0\text{-Tyr}^3\text{-Octreotate}$ and nivolumab, in patients with ES-SCLC. The primary endpoint of the phase I portion is to determine the recommended phase II doses of $^{177}\text{Lu-DOTA}^0\text{-Tyr}^3\text{-Octreotate}$ when given in combination with nivolumab. Patients with relapsed or refractory ES-SCLC and patients with advanced or inoperable grade I-II pulmonary NETs are also eligible for the phase I portion. For all patients participating in this phase I/II study, a positive SRI (Somatostatin Receptor Imaging) scan showing overexpression of SSTR2 will be mandatory for inclusion (NETSPOT®). The phase II portion will consist of patients with ES-SCLC that completed standard first-line chemotherapy with a platinum-based regimen, without disease progression (responders plus stable disease) at the time of initiation the combination therapy with $^{177}\text{Lu-DOTA}^0\text{-Tyr}^3\text{-Octreotate}$ and nivolumab. Patients will be randomly allocated in two arms: one will be treated with the combination of $^{177}\text{Lu-DOTA}^0\text{-Tyr}^3\text{-Octreotate}$ and nivolumab, and the other arm will continue be followed (observation) after completion the standard chemotherapy treatment. Cross-over will be permitted at the time of disease progression.

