After the dose finding of the phase 1 portion is concluded, the phase 2 will start. The major end of the phase I is the safety and tolerability. Activity will not be adequately assessed in the phase I portion. The total number of patients required for the whole study will be 61-64 (phase I: 9-12 patients, phase II: 52 patients).

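### The dose-escalation table gives two answers for 2 DLTs in 6 patients at 7.4 GBq, so that result does not determine the phase II dose

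*Combined protocol and SAP*

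**What the plan says.** Section 11.1 makes dose selection the phase I endpoint: "The primary endpoint of the phase I portion is to determine the recommended phase II doses". There are two dose levels. The table in section 5.3.1 lists 3.7 GBq as level 1 and "7.4 GBq (200 mCi) every 8 weeks" as level 2, and the two cumulative doses in section 9.1.1 agree with this.

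The decision rules are in the dose-escalation table of section 5.1.1.2. Two parts of it cover 2 DLTs in 6 patients at 7.4 GBq:

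- **Row for 1 DLT in 3, after the second cohort of 3.** "If 1 or more of this group suffer DLT, then dose escalation is stopped, and this dose is declared the maximally administered dose". It continues: "Three additional patients will be entered at the next lowest dose level if only 3 patients were treated previously at that dose".
- **Last row.** Its condition is "≤ 2 out of 6 at highest DL", and the decision it attaches to that result reads as follows: "This is generally the recommended phase 2 dose. At least 6 patients must be treated at the recommended phase 2 dose".

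A third row, for 2 or more DLTs, carries the same stop and step-down instructions but gives no denominator. Sections 5.1.1, 5.3.1 and 11 do not say which row prevails, or what the word *generally* depends on.

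**The concern.** A cohort rule should map every possible result to one decision before the data are seen. Here 1/3 followed by 1/3 at the top level maps to two. One row stops and goes back to 3.7 GBq; the other ends with 7.4 GBq as the usual RP2D. The step-down brings the lower level up to 6 patients, which is the minimum the plan requires at an RP2D. That has little purpose if 7.4 GBq is already the choice.

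At stake is a two-fold difference in the radionuclide dose at which phase II combination patients start. As written, someone would settle it after seeing the DLTs, with no criterion and no named decision-maker.

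**Working it through.** **Inputs**

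- Two levels: section 5.3.1. Check against section 9.1.1: 14.8/4 = 3.7 GBq and 29.6/4 = 7.4 GBq.
- Cohorts of 3, expansion to 6, at least 6 patients at the RP2D: section 5.1.1.2.
- Phase I size of 9 to 12: section 11.2.
- True DLT rates: not in the documents. I assume p = 20%, 25%, 1/3 and 40% at 7.4 GBq, with 10% as a low case, and independent patients. Write q = 1 − p.

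**Step 1. What each row decides at 7.4 GBq**

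| Result | Stopping rows | Last row | Agree? |
|---|---|---|---|
| 0/6 or 1/6 | do not apply | RP2D | yes |
| 2/6 as 1/3 then 1/3 | stop; step down if 3 at level 1 | generally RP2D | no |
| 2/6 as 0/3 then 2/3 | stop only if the row for 2 or more is read as 2 of 6 | generally RP2D | depends on reading |
| 3/6 or more | stop; step down if 3 at level 1 | does not apply | yes |

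**Step 2. Does the planned size show which reading was meant?** Ignoring replacements, the trial uses these numbers if it reaches level 2:

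- Level 1 clear at 0/3, 2/6 accepted: 3 + 6 = 9.
- Level 1 clear at 0/3, 2/6 stops: 3 + 6 + 3 = 12.
- Level 1 clear at 1/6, either reading: 6 + 6 = 12.

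The stated 9 to 12 is reproduced under both readings, so it does not settle the matter.

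**Step 3. Chance of the result, given that level 2 is reached**

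- P(1/3 then 1/3) = (3pq²)² = 9p²q⁴
- P(0/3 then 2/3) = q³ × 3p²q = 3p²q⁴

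| p | 1/3 then 1/3 | 0/3 then 2/3 | Any 2/6 |
|---|---|---|---|
| 20% | 0.147 | 0.049 | 0.197 |
| 25% | 0.178 | 0.059 | 0.237 |
| 1/3 | 0.198 | 0.066 | 0.263 |
| 40% | 0.187 | 0.062 | 0.249 |

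In the low case p = 10%, the first path has probability 9 × 0.01 × 0.6561 = 0.059.

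**Step 4. Unconditional chance of 1/3 then 1/3.** With level 1 rate p₁ and q₁ = 1 − p₁, P(reach level 2) = q₁³ + 3p₁q₁⁵. The step-down is triggered only if level 1 cleared at 0/3, which has probability q₁³.

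| p | Path, p₁ = p/2 | with step-down | Path, p₁ = p | with step-down |
|---|---|---|---|---|
| 20% | 0.906 × 0.147 = 0.134 | 0.107 | 0.709 × 0.147 = 0.104 | 0.075 |
| 25% | 0.862 × 0.178 = 0.153 | 0.119 | 0.600 × 0.178 = 0.107 | 0.075 |
| 1/3 | 0.780 × 0.198 = 0.154 | 0.114 | 0.428 × 0.198 = 0.084 | 0.059 |
| 40% | 0.709 × 0.187 = 0.132 | 0.096 | 0.309 × 0.187 = 0.058 | 0.040 |

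**Step 5. Effect on selecting 7.4 GBq, given that level 2 is reached**

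- All 2/6 rejected: P(≤ 1/6) = q⁶ + 6pq⁵
- Only 0/3 then 2/3 accepted: add 3p²q⁴
- All 2/6 accepted: add 12p²q⁴ to the first line

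| p | All 2/6 rejected | Only 0/3 then 2/3 accepted | All 2/6 accepted |
|---|---|---|---|
| 20% | 66% | 70% | 85% |
| 25% | 53% | 59% | 77% |
| 1/3 | 35% | 42% | 61% |
| 40% | 23% | 30% | 48% |

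The last two columns differ by the undisputed conflict, the 1/3-then-1/3 path. The first and last differ by every 2/6 result.

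**The case against.** The best counter-argument is that the rows answer different questions. The stopping rows end escalation and attach a label; they never say the dose is too toxic or cannot be the RP2D. With two levels, 7.4 GBq is the highest dose given in any case. The last row alone names the RP2D and alone is limited to the top level, so it could be read as the specific rule that prevails. The DLT definition in section 5.1.1.1 is broad (grade 2 platelet toxicity counts), so room for judgement at 2/6 is defensible. Section 12.4 provides monthly safety teleconferences and quarterly committee review, and individual patients can be reduced to 3.7 GBq.

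Some of this stands. The label by itself can coexist with selection as RP2D. The enrolment instructions collide only if level 1 cleared at 0/3. If 6 patients were already treated there, what remains is one row treating 2/6 as a stop and the other as usually acceptable. The 0/3-then-2/3 path is in dispute only on one reading of the row without a denominator. The rates are assumed, and at 10% the problem is small. The phase II comparison, with its 40 events and 52 patients, is untouched.

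It does not remove the conflict. The coexistence reading does not explain why the lower level is filled to the number required at an RP2D. The specific-over-general reading is not written down, and *generally* leaves the choice open even then. Committee review and individual reductions limit harm, but they do not say which dose phase II opens with.

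**Conclusion.** The concern holds. The table is wrong as written: for 1/3 then 1/3 at 7.4 GBq it sets two conflicting thresholds for the phase I primary endpoint. At assumed true DLT rates of 20% to 40%, that sequence arises in 15% to 20% of trials that reach 7.4 GBq. Unconditionally the figure is 13% to 15% if the level 1 rate is half the level 2 rate, and 6% to 11% if the rates are equal. The sharpest form, with the step-down triggered, has unconditional probability 10% to 12% or 4% to 8% respectively. Given that level 2 is reached, the row applied changes the chance that 7.4 GBq is selected by 15 to 20 percentage points, or by 20 to 26 if the 0/3-then-2/3 path is also disputed. These sizes rest on the assumed rates and on independent patients; the contradiction itself rests only on the text.

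**What to change.** Before DLT data at 7.4 GBq are seen, give 2/6 at the highest level one decision:

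- **(a)** change the last row to at most 1 DLT in 6, in line with the stopping rows; or
- **(b)** keep at most 2 in 6, and state that the highest level is exempt from the stop-and-step-down instructions.

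Either way, give the row for 2 or more DLTs a denominator. Delete *generally*, or say who decides and on what grounds. Which threshold is right is a clinical choice for the sponsor's team.

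The cost is a wording change to one table, with IRB approval of the amendment under section 12.6. Either rule fits the planned 9 to 12 phase I patients: 3 + 6 + 3 = 12 with a step-down, 6 + 6 = 12 if both levels are expanded. Phase II numbers do not change.
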